Vaccination Procedure:

All eligible subjects will receive one intramuscular vaccination (into the deltoid area of the non-dominant arm) with GVGH *S. sonnei* 1790GAHB vaccine containing 25µg/dose. Subjects will be observed at the clinic site for 4 hours after vaccination.

Procedure for Collection of Solicited AEs:

Beginning in the evening following study vaccine administration (approximately 6 hours), and daily during the following 6 days following vaccination, diary cards will be used to collect solicited local and systemic adverse events including other reactions (i.e. body temperature measurements and use of analgesics/antipyretics). A reminder phone call will be performed or an email will be sent by the site staff to the subject 2 and 6 days following vaccination to remind subjects that the diary card should be completed (no update on the status of the subject's health will be solicited during these contacts that are not intended for safety data collection).

Seven days following vaccination, a clinical visit (Visit 2) will be performed at the study site and all information recorded in the diary card will be reported on e-CRF in order to document all safety data occurred during the one week follow-up post vaccination.

In addition to the solicited adverse events data, any unsolicited AE, solicited local and systemic AE that continue at 7 days after study vaccination (Visit 2), will be collected and recorded at V2, V3 and V4 by clinical study staff in the subject's source document. All Serious Adverse Events (SAEs), all AEs leading to vaccine/study withdrawal, all Adverse Events of Special Interest (AESI, see below) and all concomitant medications associated with those events, will be collected and recorded in the subject's source document and on an Adverse Events CRF(s) from the time of vaccination (visit 1) to study termination (visit 5). These data will be captured through interview of the subject and by review of available medical records.

Reactive arthritis and neutropenia will be collected and analyzed as AESIs for this study.

A summary of the main medical and safety data to be collected into the e-CRF during the study is provided in [Table 2](#).

Name of Sponsor: GlaxoSmithKline Biologics SA (GSK Bio)	Protocol number: H03_01E1TP	Generic name of study vaccine(s): GVGH Shigella sonnei 1790GAHB vaccine
Study Vaccines: GVGH S. sonnei (1790GAHB) vaccine		

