		1	3, 7 V1+2 days; V1+6 days	8 V1+7 days	15 V1+14 days	29 V1+28 days	85 V1+84 days	
		Visit Window (Days)	-21 to -1	n/a	n/a	0 to +1	0 to +4	-3 to +7
Visit Number		Screening	1		2	3	4	5
Study Event	References							
Study Treatment								
Vaccination	Section 5.2		X					
Screening and Safety								
Informed Consent ^a	Section 5.1.1	X						
Medical History	Sections 5.1.2	X						
Physical Exam ^b	Sections 5.1.2 and 5.1.3	X	X					
Symptom-directed physical Exam ^b	Section 5.3.1				X	X	X	X

Vital signs (temperature, respiratory rate, heart rate, blood systolic and diastolic pressure)	Sections 5.1.2 Screening and 5.2.1 Post-vaccination Procedures	X	X					
Safety blood draw (Hematology)	Sections 3.5 and 7.1.7	X			X			X

Visit Type Study Day Visit Window (Days) Visit Number	Clinic Visit	Clinic Visit	Phone Call	Clinic Visit	Clinic Visit	Clinic Visit	Clinic Visit	Clinic Visit	
		1	3, 7 V1+2 days; V1+6 days	8 V1+7 days	15 V1+14 days	29 V1+28 days		85 V1+84 days	
	-21 to -1	n/a	n/a	0 to +1	0 to +4	-3 to +4		-3 to +7	
	Screening	1		2	3	4		5	
Study Event	References								
Serology (HIV, hepatitis B and C, and HLA-B27 testing only for naïve subjects) ^d	Section 3.5 and 5.1.2	X							
Pregnancy Test	Sections 3.5 and 5.1.2		X					X	
Exclusion/Inclusion Criteria	Section 4	X							
Post Injection Assessment ^e	Section 5.2.1		X						
Subject Diary Dispensed with Training	Section 5.2.1		X						

Subject Diary Reminder Call	Section 5.2.2			X				
Subject Diary Reviewed and Collected	Section 5.3.1				X			
Assess all AEs	Section 7.1	X	X		X	X	X	
Assess SAEs	Section 7.1.4	X	X		X	X	X	X
Assess for NOCDs, medically attended AEs, AEs leading to withdrawal, and AESIs	Sections 7.1.4.1 and 7.1.3		X		X	X	X	X

Number	Study Event	Visit Type	Clinic Visit	Clinic Visit	Phone Call	Clinic Visit	Clinic Visit	Clinic Visit
		Study Day		1	3, 7 V1+2 days; V1+6 days	8 V1+7 days	15 V1+14 days	29 V1+28 days
		Visit (Days)	-21 to -1	n/a	n/a	0 to +1	0 to +4	-3 to +4
		Window	Screening	1		2	3	4
Visit	References							
Assess relevant medications	Sections 5.1.2 and 6.5	X	X		X	X	X	X
Immunogenicity								
Serology blood draw	Section 3.5		X		X	X	X	X

Additional blood draw for preparation of standard serum	Section 3.5						X	
Study Completion Procedures								
Study Termination ^f	Section 5.5							X

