A blood sample will be obtained as part of the initial screening for hematology and serology (HIV, hepatitis B and C, and for HLA-B27 testing only for naïve subjects). Blood will be collected for hematology also on day 8 and 85 (visit 2 and 5 respectively). Each consented subject will have blood collected before vaccination on day 1 for baseline immunological testing and on day 8, 15, 29 and 85 (visit 2, 3, 4, and 5 respectively) post vaccination for immunological. Additional blood draw for preparation of standard serum will be done on day 29 post vaccination (visit 4). Urine pregnancy test will be done at visit 1 prior to vaccination and at visit 5. All individuals with neutropenia occurring at any time during the study will have additional blood draws to repeat complete blood count on a weekly basis until the neutropenia resolves. If neutropenia occurs at the last study visit, Complete Blood Count to be repeated on a regular basis until resolution (for classification of neutropenia during the trial, refer to [Section 5.4 Unscheduled Visits](#)).

Subjects will be observed at the clinic for 4 hour after vaccination on visit 1. Vital signs will be collected before vaccination and at 30 minutes and 4 hours post vaccination. Before leaving the clinic, they will be given a paper dairy card and trained to record in any adverse events occurring before visit 2 and will be reminded by phone call or email on day 3 and 7 post vaccination. These dairy cards will be collected and reviewed on day 8 post vaccination (visit 2).

Any unsolicited AE until visit 4, SAEs until study termination, all AEs leading to study withdrawal, reactive arthritis and severe neutropenia (AESI) and all concomitant medications associated with those events, will be collected and recorded in the subject's source document and in the eCRF. Further details on study procedure are found in [sections 5, Study Procedures and 7, Assessments](#).

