7. ASSESSMENTS

7.1 Safety Assessment

The measures of safety used in this study are based on previous study data. They include a close vigilance for, and stringent reporting of selected local and systemic adverse events routinely monitored in vaccine studies as indicators of reactogenicity.

An adverse event (AE) is defined as any untoward medical occurrence in a subject or clinical investigation subject administered a pharmaceutical product at any dose that does not necessarily have to have a causal relationship with this treatment. Therefore, an AE can be any unfavorable and unintended sign (including an abnormal laboratory finding, for example), symptom, or disease temporally associated with the use of an investigational product, whether or not considered related to the investigational product. This definition includes intercurrent illnesses or injuries and exacerbation of pre-existing conditions.

For the purpose of this trial, AEs will be from the time the subject signs informed consent until Visit 4. AEs occurring after the informed consent form is signed but prior to receiving study vaccine will be documented as an adverse event and recorded within source document. However, any AEs occurring prior to receipt of any study vaccine will be analyzed separately from “treatment emergent” AEs (AEs occurring after administration of the first study vaccine). All adverse events that are serious, clinically significant as judged by the investigators, medically attended and AESI will be collected until study termination at visit 5.

Adverse events are collected as either solicited or unsolicited adverse events. Solicited events are derived from organized data collection systems, such as Subject Diaries or interview.

7.1.1 **Solicited Adverse Events**

The term “reactogenicity” refers to solicited signs and symptoms (“solicited adverse events”) occurring in the hours and days following a vaccination, to be collected by the subject for 7 consecutive days, using a pre-defined Subject Diary.

The following solicited adverse events are included in the Subject Diary. Each adverse event is to be assessed using the scoring system reported in parentheses below:

Solicited Local Adverse Events

These include erythema, induration and pain at injection site. They will be assessed using the scoring system reported in a table below. **Table 6 Grading of solicited local adverse events**

Solicited local adverse events	Grade 0 Absent	Present - Grading of Severity		

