7.1.4.1 Adverse Events of Special Interest

Adverse events of special interest (AESIs) are predefined adverse events that will be specifically highlighted to the investigator and will be summarized separately. Only AESI meeting the definition of SAE will be categorized and reported as such in this study.

Reactive arthritis (ReA) or Neutropenia will be collected and analyzed as an AESI for this study.

Reactive arthritis is defined as non-purulent joint inflammation that develops in response to an infection in another part of the body. Since the inflammation is triggered by a previous condition, it is termed “reactive”. Intestinal pathogens that have been associated with reactive arthritis include *Campylobacter*, *Salmonella*, *Yersinia*, *Clostridium difficile*, and *Shigella*. If reactive arthritis is caused by an auto immune response, there is at least a possibility that it could be initiated by vaccination of susceptible people with the 1790GAAH vaccine.

For diagnosis of ReA, imaging and aspiration are not required (unless clinically indicated).

Neutropenia is defined as decrease of neutrophil count asymptotically or symptomatically with ANC $<1.8 \times 10^9/L$, occurring at 7 days after vaccination. Its graded from grade 1 to 4 basing on neutrophil counts as follows: Grade 1 ANC $1.5- <1.8 \times 10^9/L$, Grade 2 ANC $<1.5 \times 10^9/L$, Grade 3 ANC $1.0- 0.5 \times 10^9/L$, and Grade 4 $<0.5 \times 10^9/L$.

This is completely diagnosed by laboratory testing for complete blood count.

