Clinically significant modifications in hematology will be assessed by medical judgment and recommendations from CBER FDA guidance for Industry; Toxicity Grading

Vaccination Procedure:

All eligible subjects will receive one intramuscular vaccination with GVGH *S. sonnei* 1790GAHB vaccine. Subjects will be observed at the clinic site for 4 hours after vaccination. Safety procedures:

All subjects providing informed consent will undergo review of medical history, a general physical examination including vital signs measurement (temperature, respiratory rate, heart rate, blood systolic and diastolic pressure) at the screening visit (study Days 21 to-1)

and at Visit 1 (Day 1). At clinic Visit 2 and at subsequent visits, a brief symptom-directed physical examination (if necessary according to symptoms the subject has reported) will be performed.

For all women of childbearing potential before vaccination at visit 1, a urine pregnancy test will be conducted and will also be repeated at visit 5 (Day 85).

Procedure for Collection of Solicited AEs:

Beginning in the evening following study vaccine administration (approximately 6 hours), and daily during the 6 days following vaccination, diary cards will be used to collect solicited local and systemic adverse events including other reactions (i.e. body temperature measurements and use of analgesics/antipyretics).

A reminder phone call will be performed or an email will be sent by the site staff to the subject 2 and 6 days following vaccination to remind subjects that the diary card should be completed. Seven days following vaccination, a clinical visit (Visit 2) will be performed at the study site and all information recorded in the diary card will be reported on e-CRF.

In addition to the solicited adverse events data, any unsolicited AE, solicited local and systemic AE that continue at 7 days after study vaccination (Visit 2), will be collected and recorded at V2, V3 and V4 by clinical study staff.

All Serious Adverse Events (SAEs), all AEs leading to vaccine/study withdrawal, all Adverse Events of Special Interest (AESI, see below) and all concomitant medications associated with those events, will be collected from the time of vaccination (visit 1) to study termination (visit 5).

Reactive arthritis and neutropenia will be collected and analyzed as AESIs for this study.

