4. ENDPOINTS

Primary Efficacy/Safety Endpoint(s):

This study has no primary efficacy or safety endpoints.

Primary Immunogenicity Endpoint(s)

Memory response, against the OAg of *S. sonnei* will be evaluated by measuring IgG Geometric mean concentrations (GMCs) 7 days after vaccination as determined by ELISA with O-antigen containing LPS as coating antigen.

Secondary safety endpoint(s):

The measures of safety will include:

- a. Numbers of subjects with deviations from normal values of hematological tests after vaccination.
- b. Numbers of subjects with solicited local and systemic reactions during 7 days following vaccination. Solicited local reactions include injection site erythema, injection site induration and injection site pain; solicited systemic reactions include headache, arthralgia, chills, fatigue, malaise, myalgia, and fever (as measured orally).
- c. Numbers of subjects with reported unsolicited adverse events (of any nature and severity) during 84 days following vaccination.

d. Number of subjects with reported SAEs throughout the study duration.

Secondary Immunogenicity Endpoint(s)

- a. IgG Geometric mean concentrations (GMCs) at 7, 14, 28 and 84 days after vaccination as determined by ELISA and applicable geometric mean ratios between post vaccination and baseline samples.
- b. Number and percentage of subjects with seroresponse for anti- LPS *S. sonnei* at 7, 14, 28 and 84 days after vaccination. Seroresponse is aimed to define a significant increase in post vaccination samples based on the biological performance of this specific serology assay and it is defined as follows:
 - If the baseline value is greater than 50 ELISA Units (EU) then an increase of at least 50% in the post-vaccination sample as compared to baseline [i.e. $((\text{Post-vac} - \text{baseline})/\text{baseline})100\% \geq 50\%$].
 - If the baseline value is less or equal to 50 EU then an increase of at least 25 EU in the post-vaccination sample as compared to baseline [i.e. $(\text{Post-vac} - \text{baseline}) \geq 25 \text{ EU}$].
- c. Number and percentage of subjects with titers post vaccination concentration ≥ 121 EU/ml for anti-LPS *S. sonnei* at 7, 14, 28 and 84 days after vaccination.

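### Secondary safety endpoint (c) promises 84 days of all unsolicited AEs, but general collection stops at Visit 4 (28 of 84 days) and the SAP tabulates both periods as one interval

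*SAP*

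**What the plan says.** All protocol references are to Version 2.

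**Endpoint.** The synopsis, Protocol 8.1.2.1 and SAP section 4 define endpoint (c) as "Numbers of subjects with reported unsolicited adverse events (of any nature and severity) during 84 days following vaccination".

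**Collection.** The synopsis and SAP section 2 say that unsolicited AEs "will be collected and recorded at V2, V3 and V4 by clinical study staff". Protocol 7.1 says that "AEs will be from the time the subject signs informed consent until Visit 4". Protocol 3.1 gives the scope as "Any unsolicited AE until visit 4, SAEs until study termination, all AEs leading to study withdrawal, reactive arthritis and severe neutropenia (AESI", the last two items being its AESIs. In Table 2 the row for assessing all AEs is marked up to Visit 4 and blank at Visit 5, whereas the SAE row is marked at Visit 5.

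**After Visit 4.** Protocol 7.1 continues with events that are "serious, clinically significant as judged by the investigators, medically attended and AESI will be collected until study termination at visit 5". Table 2 marks a different row at Visit 5: "Assess for NOCDs, medically attended AEs, AEs leading to withdrawal, and AESIs". The Visit 5 interview in Protocol 5.5 names those categories plus SAEs.

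**Analysis.** SAP 6.5.2.3 summarises any unsolicited AE over a single period from Day 1 to study termination, and Annex 2 Table 12-1 has one unsolicited safety set for the whole study. Protocol 8.4.2.1.3 calls for summaries by observation interval without saying what the intervals are. SAP section 9 records no change from the planned analyses.

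**The concern.** The endpoint describes an 84-day count of every unsolicited AE. The procedures collect that for the first third of the period only. For the rest, a mild event that is not medically attended, and falls into none of the other selected categories, is not systematically sought. Placing both periods in one table, labelled as the whole study, hides the change of rule from anyone who reads the resulting percentage.

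A descriptive safety trial delivers the stated rates, so a rate whose label does not match its ascertainment is a real defect even with no hypothesis test. Two features of the SAP carry it further. Section 6.5.2.3 does not list medically attended AEs or new onset of chronic disease as separate categories, although Protocol 8.4.2.1.3 does. Non-serious events of these kinds after Visit 4 may therefore appear only in the mixed table. Section 6.5.2.4 also prepares a combined non-serious AE summary for registry posting and states no onset interval.

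**Working it through.** **Inputs (Protocol Table 2).** Visit 1 is Day 1. Visit 4 is Day 29, window -3 to +4 days. Visit 5 is Day 85, window -3 to +7 days. The endpoint period is 84 days.

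**1. The plan's own figure.** Visit 5 minus Visit 1: 85 - 1 = 84 days. The 84 days match total follow-up.

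**2. Period with general AE collection.** Visit 4 minus Visit 1: 29 - 1 = 28 days, and 28/84 = 33.3%. This does not match 84.

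**3. Visit 4 window.** Earliest 28 - 3 = 25 days (25/84 = 29.8%); latest 28 + 4 = 32 days (32/84 = 38.1%). No permitted Visit 4 date comes near 84.

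**4. Remainder with selected categories only.** Nominal 84 - 28 = 56 days (66.7%); range 84 - 32 = 52 days (61.9%) to 84 - 25 = 59 days (70.2%).

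**5. End of the SAP interval.** Study termination is Visit 5, so the interval ends between 84 - 3 = 81 and 84 + 7 = 91 days after vaccination. It need not equal the 84 days in the endpoint.

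**6. Categories followed to Visit 5.**

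| Category | Protocol 7.1 | Table 2 and Protocol 5.5 |
|---|---|---|
| SAE | yes | yes |
| AESI | yes | yes |
| Medically attended | yes | yes |
| Clinically significant, investigator's judgement | yes | not named |
| Leading to withdrawal | not named | yes |
| New onset of chronic disease | not named | yes |

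The AESI row is not clean either. Protocol 3.1 speaks of severe neutropenia. Protocol 7.1.4.1 says "Reactive arthritis (ReA) or Neutropenia will be collected and analyzed as an AESI for this study" with no severity limit, but then ties the definition of neutropenia to 7 days after vaccination.

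**7. Illustration of scale, not an estimate.** The documents give no AE rate. Assume that the AEs not followed after Visit 4 occur at a constant rate, independently over three 28-day blocks. A 28-day subject risk p then implies an 84-day risk of 1 - (1 - p)^3:
- p = 5%: 14.3%, of which the first 28 days hold 5/14.3 = 35%.
- p = 20%: 48.8%, share 41%.
- p = 40%: 78.4%, share 51%.

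If the rate falls with time since vaccination, or the same subjects report repeatedly, the gap is smaller.

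**The case against.** The strongest case on the other side has four parts.

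*Collection may in practice continue.* Protocol 5.2.1 and 7.1.2 have unsolicited AEs collected at the next visit without naming a last one, 5.3.1 lists Day 85 as a safety follow-up visit, and the Visit 5 procedures include a review of systems. These are general procedures. They do not displace the explicit Visit 4 limit in 3.1 and 7.1 or the blank Table 2 cell. What stands is that sites could read the cut-off differently, which supports reconciling the text.

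*The endpoint says reported events.* It also says any nature and severity over 84 days, and a reader will take that as complete ascertainment.

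*The trial is descriptive and the schedule is common to all groups.* This largely stands. Contrasts between previously vaccinated and unvaccinated subjects are little affected, SAEs have their own endpoint, SAEs and AESIs have their own summaries, and Protocol 8.4.2.1.3 provides by-subject listings. One small exception is that the early termination visit (5.5.1) asks about unsolicited AEs, so a subject leaving between Visits 4 and 5 is asked more than one who completes.

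*The protocol does not demand a split at Visit 4.* Correct. A reader might infer from Protocol 8.4.2.1.3 that the SAP breaches a required interval, but that section defines none. A Visit 4 split fits its wording and is a recommendation.

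A reader might also infer that the reported count can only be too low. The documents do not support that. SAP 6.5.2.3 merges solicited events continuing beyond day 7 into the unsolicited events, Protocol 3.4.2 records verbally reported solicited events as unsolicited, and a late Visit 5 can admit events from days 85 to 91.

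**Conclusion.** The mismatch is real in the current text of both documents. Endpoint (c) states 84 days for all unsolicited AEs. The procedures give full ascertainment for 28 days (33%; 25 to 32 days, 30% to 38%, across the Visit 4 window), and the SAP reports both periods under one label. The table as planned cannot be read as an 84-day incidence of all AEs.

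This conclusion assumes that sites follow the explicit Visit 4 limit. The likely net effect is under-counting of non-selected AEs after Visit 4. Its size cannot be derived, and the merged solicited events and the Visit 5 window also move the count.

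The differing category lists are a secondary matter. It is tempting to set every statement of what is collected against every other and count disagreements. The documents do not support such a count: the synopsis refers on to Table 2, and Protocol 3.1 refers on to sections 5 and 7 and attaches study termination to SAEs alone. The substantive conflict is Protocol 7.1 against Table 2 and 5.5.

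The point should be fixed, but it concerns one secondary safety endpoint and leaves the primary immunogenicity objective untouched.

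**What to change.** 1. **SAP 6.5.2.3.** Tabulate all unsolicited AEs with onset from Day 1 to Visit 4. Separately, to Visit 5, tabulate only the categories collected to Visit 5. State the ascertainment in each table title, align Annex 2, and record the change in SAP section 9.

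2. **Endpoint (c).** Make the window agree with the collection period in the synopsis, Protocol 8.1.2.1 and SAP section 4. The documents do not show which was intended. If the Visit 4 limit was, state Day 1 to Visit 4 for AEs of any nature and severity. If 84 days was, collect all unsolicited AEs to Visit 5. If the wording is left alone, step 1 with clear labels is the minimum.

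3. **Supporting text.** Reconcile Protocol 7.1 with Table 2 and 5.5, the neutropenia wording in 3.1 with 7.1.4.1, and the early termination visit in 5.5.1 with the Visit 5 interview in 5.5. State the Visit 4 limit in 5.2.1, 5.3.1 and 7.1.2 if it is kept.

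**Cost.** Step 1 needs SAP text, labels and a few more tables. The table to Visit 4 uses data already planned; the table to Visit 5 depends on what sites actually collected. Shortening the endpoint reduces the stated all-AE window from 84 to 28 days and may need an amendment under Protocol 13.4. Keeping 84 days needs added data collection.
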